### 6.4.2 Laboratory Data

The list of parameters to be measured (biochemical, hematological, coagulation and urine), systemic lupus erythematosus (SLE) is provided in the following table. Clinical laboratory values will be expressed using conventional SI units for the analysis as defined by the SDTM Controlled Terminology.

**Table 11 Clinical Laboratory Tests and SI units**

Blood Chemistry (serum) (SI unit):	
Blood urea nitrogen (BUN) (mMol/L)	Calcium (mmol/L)
Glucose (random) (mmol/L)	eGFR (mL/min/1.73m  )
Glucose (fasting)	AST (U/L)
Creatinine (umol/L)	ALT (U/L)
Creatine kinase (U/L)	ALP (U/L)
Creatinine Kinase-MB (ug/L)	Total protein (g/L)
Total IgG (umol/L)	Total bilirubin (umol/L)
Potassium (mmol/L)	Direct bilirubin (umol/L)
Sodium (mmol/L)	c-reactive protein (mg/L)
Hematology (SI unit):	
Red blood cells (x 10  /L)	Reticulocytes/Erythrocytes (%)
Platelets (x10  /L)	Reticulocytes (10  /L)

Hemoglobin (g/L)	Neutrophils (x10  /L) Neutrophils/Leukocytes (%)
Hematocrit (packed cell volume [PVC]) (%)	Eosinophils (x10  /L) Eosinophils /Leukocytes (%)
Mean cell volume (MCV) (fL)	Lymphocytes (x10  /L) Lymphocytes/Leukocytes (%)
Mean cell hemoglobin (MCH) (pg)	Basophils (x10  /L) Basophils /Leukocytes (%)
White blood cells (10  /L)	Monocytes (x10  /L) Monocytes/Leukocytes (%)
Coagulation	
International normalized ratio	
Urinalysis	
pH	Nitrite
Specific gravity	Leukocyte esterase
Glucose	White blood cells
Protein	Crystals
Blood	Casts
Ketones	Epithelial cells
Bilirubin	Yeast cells
Urobilinogen	
Pregnancy test	
Pregnancy test	FSH (IU/L)
SLE panel	
ANA	If the SLE panel detects ANA, additional autoantibodies (anti-dsDNA, anti-Smith, anti-phospholipid (anti-cardiolipin IgG and anti-beta-2- glycoprotein IgG), anti-Ro (anti-Ro52 and anti-Ro60), anti-La and anti-U1RNP) will be evaluated.

All clinical laboratory parameters will be summarized in the SAF set on the DBTP and the safety follow-up period.

In the event of repeat values, the last non missing value per visit will be used. In the case of a protocol specified laboratory result being of the form “<x”, to include in continuous summaries, the numeric result will be derived as x. For results reported as “>x”, the numeric result will be derived as x.

For each quantitative laboratory parameter (chemistry, hematology, coagulation and urinalysis), the actual value and change from baseline at each visit/time point on DBTP will be summarized by treatment group using descriptive statistics.

All laboratory data will be listed, but only for participants with any postbaseline abnormality or toxicity grade  $\geq 1$ .

For laboratory parameters with no toxicity grades results will be categorized according to reference ranges from the central laboratory using non imputed value and limits as:

Low if parameter result is < Lower Limit of Normal (LLN)

High if parameter result is > Upper Limit of Normal (ULN)

Normal if parameter value is within normal range ( $LLN \leq \text{result} \leq ULN$ )

Treatment-emergent out-of-range values are defined as laboratory values:

- with normal values at baseline and low or high value at any post baseline visit, or
- with low values at baseline and high at any post baseline visit, or
- with high values at baseline and low at any post baseline visit.

If baseline is missing, any post-baseline abnormality will be considered treatment emergent.

For parameters with toxicity grades (Table 12), Treatment-emergent toxicity grade values are defined as laboratory values with higher grade post-baseline compared to the grade at baseline. If baseline is missing any postbaseline toxicity will be considered treatment-emergent.

The CTCAE Version 5.0 will be used as the basis for toxicity grading. CTCAE grades will be programmatically derived as described in the Table 12 when applicable.

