**Table 12 Toxicity Grading for Selected Laboratory Tests**

Parameter	Unit	Grade 1	Grade 2	Grade 3	Grade 4
Alanine amino transferase (ALT)		>1-3 *ULN	>3-5 *ULN	>5-20 *ULN	>20 *ULN
Alkaline phosphatase (ALP)		>1.0-2.5 *ULN	>2.5-5.0 *ULN	>5.0-20.0 *ULN	>20.0 *ULN
Aspartate amino transferase (AST)		>1-3 *ULN	>3-5 *ULN	>5-20 *ULN	>20 *ULN
Bilirubin (total)		>1.0-1.5 *ULN	>1.5-3.0 *ULN	>3.0-10.0 *ULN	>10.0 *ULN
Creatine kinase		>1.0-2.5 *ULN	>2.5-5.0 *ULN	>5.0-10.0 *ULN	>10.0 *ULN

Paramater	Unit	Grade 1	Grade 2	Grade 3	Grade 4
Creatinine		>1.0-1.5 *ULN	>1.5-3.0 *ULN	>3.0-6.0 *ULN	>6.0 *ULN
Glucose (fasting) low	mmol/L	<LLN-3.0	<3.0-2.2	<2.2-1.7	<1.7
	mg/dL	<LLN-55	<55-40	<40-30	<30
Potassium low	mmol/L	-	<LLN-3.0	<3.0-2.5	<2.5
	mEq/L	-	<LLN-3.0	<3.0-2.5	<2.5
Potassium high	mmol/L	>ULN-5.5	>5.5-6.0	>6.0-7.0	>7.0
	mEq/L	>ULN-5.5	>5.5-6.0	>6.0-7.0	>7.0
Sodium low	mmol/L	<LLN-130	-	<130-120	<120
	mEq/L	<LLN-130	-	<130-120	<120
Sodium high	mmol/L	>ULN-150	>150-155	>155-160	>160
	mEq/L	>ULN-150	>150-155	>155-160	>160
International normalized ratio		>1.2-1.5 *ULN	>1.5-2.5 *ULN	>2.5 *ULN	-
Lymphocytes (absolute count) low	giga/L	<LLN-0.80	<0.80-0.50	<0.50-0.20	<0.20
	counts/mm 	<LLN-800	<800-500	<500-200	<200
Lymphocytes (absolute count) high	giga/L	-	>4-20	>20	-
	counts/mm 	-	>4000-20000	>20000	-
Neutrophils (absolute count) low	giga/L	<LLN-1.5	<1.5-1.0	<1.0-0.5	<0.5
	counts/mm 	<LLN-1500	<1500-1000	<1000-500	<500
Platelets	giga/L	<LLN-75	<75-50	<50-25	<25
	counts/mm 	<LLN-75000	<75000-50000	<50000-25000	<25000
White blood cells	giga/L	<LLN-3	<3-2	<2-1	<1
	counts/mm 	<LLN-3000	<3000-2000	<2000-1000	<1000

If grade is different from grade 1 to 4, grade will be assigned to 0.

For non gradable parameters per NCI CTCAE grading system, shift tables will be created to summarize the number and proportion of participants with shifts from baseline category to post baseline category (“Low”, “Normal”, “High”, treatment-emergent out-of-range) by treatment group and visit. Shift tables from baseline to worst postbaseline category will also be presented. In case of low and high post-baseline values, a category ‘low + high’ will be defined.

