For laboratory parameters which can be graded per NCI CTCAE grading system, the information will be summarized using a shift table summarizing the baseline NCI CTCAE grade (0,1,2,3,4) versus post baseline category NCI CTCAE grade by treatment group and visit. Shift tables from baseline to worst post DBTP baseline NCI CTCAE grade will also be displayed. If there is no evaluation, the worst grade will be set to ‘Missing’. Parameters with toxicity grades defined in both directions (decreased and increased) will be shown by direction. Numbers and cumulative numbers over decreasing toxicities grading of participants with treatment-emergent toxicities will also be shown.

All laboratory data will be listed, but only for participants with post baseline abnormalities or toxicity grade  $\geq 1$ .

For ANA titers (SLE panel), the number and percentage of participants will be summarized by category at each visit in SAF set on DBTP. The following categories for ANA titers will be defined:

- Negative, in case of negative result
- Positive:

I	
I	

In case of multiple titers results for the same assessment, the worst assessment (ie most positive) should be considered.

Shift tables from baseline to worst post baseline category (“Negative”, “ Low positive” and “High positive”) will also be presented.

A listing of participants with ANA titer  $> 1:80$  will be provided and will include the following assessments: anti-dsDNA, anti-Smith, anti-phospholipid (anti-cardiolipin IgG and anti-beta-2- glycoprotein IgG), anti-Ro (anti-Ro52 and anti-Ro60), anti-La and anti-U1RNP.

A listing of Laboratory results for participants entering into the SFU period will be provided.

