Table	14.3.4.1.1	Blood Chemistry: Summary of Laboratory Test Results and Change from Baseline by Visit during DBTP - Safety Set		x	x
Table	14.3.4.1.2	Blood Chemistry - Shift Table of Reference Ranges versus Baseline during DBTP - Safety Set		x	x
Table	14.3.4.1.3	Blood Chemistry - Shift Table of Laboratory Toxicity Grades versus Baseline during DBTP - Safety Set		x	x
Table	14.3.4.1.4	Hematology: Summary of Laboratory Test Results and Change from Baseline by Visit during DBTP - Safety Set		x	x
Table	14.3.4.1.5	Hematology - Shift table of Reference Ranges versus Baseline during DBTP - Safety Set		x	x
Table	14.3.4.1.6	Hematology - Shift table of Laboratory Toxicity Grades versus Baseline during DBTP - Safety Set		x	x

Table	14.3.4.1.7	Coagulation: Summary of Laboratory Test Results and Change from Baseline by Visit during DBTP and Safety Follow-up period - Safety Set		x	x
Table	14.3.4.1.8	Coagulation - Shift table of References Ranges versus Baseline on Clinical Findings during DBTP and Safety Follow-up period Period - Safety Set		x	x
Table	14.3.4.1.9	Urinalysis: Summary of Laboratory Test Results and Change from Baseline by Visit during DBTP - Safety Set		x	x
Table	14.3.4.1.10	Urinalysis - Shift table of Reference Ranges versus Baseline during DBTP - Safety Set		x	x
Table	14.3.4.1.11	Antinuclear Antibodies (ANA) - Proportions by Categories during DBTP - Safety Set		x	x
Table	14.3.4.1.12	Antinuclear Antibodies (ANA) - Shift table of ANA categories versus Baseline during DBTP - Safety Set		x	x
VITAL SIGNS					
Table	14.3.4.2.1	Summary of Vital Signs and Change from Baseline by Visit during DBTP and Safety Follow-up period - Safety Set		x	x
Table	14.3.4.2.2	Vital Signs - Shift Table of vital signs abnormalities versus Baseline Visit during DBTP and Safety Follow-up period – Safety Set		x	x
ECG					
Table	14.3.4.3.1	Summary of ECG and Change from Baseline by Visit during DBTP - Safety Set		x	x
Table	14.3.4.3.3	ECG - Shift Table of abnormalities versus Baseline during DBTP - Safety Set		x	x

Table	14.3.4.3.4	ECG - Shift Tables of QTC Abnormalities versus Baseline – Safety Set		x	x
Table	14.3.4.3.5	ECG - Proportions of QTC Change abnormalities by Categories and by Visit during DBTP - Safety Set			x
OTHER SAFETY					
Table	14.3.4.4.1	Number of Participants with Suicidal Ideation during DBTP - Safety Set		x	x

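### Section 6.4.2 requires a toxicity-grade shift table for INR, but Table 24 lists only a reference-range shift table for coagulation, for which INR does not qualify

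*SAP*

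**What the plan says.** **Which test.** Table 11 has one entry under coagulation, INR. Table 12 includes "International normalized ratio" with grade 1 at >1.2-1.5, grade 2 at >1.5-2.5 and grade 3 at >2.5 times ULN, and no grade 4. A value that meets none of the grades is assigned grade 0.

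**Which rule.** Section 6.4.2 divides the laboratory tests in two.

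- Ungraded tests: "For laboratory parameters with no toxicity grades results will be categorized according to reference ranges from the central laboratory". Their output is described as "For non gradable parameters per NCI CTCAE grading system, shift tables will be created to summarize the number and proportion of participants with shifts".
- Graded tests: "For laboratory parameters which can be graded per NCI CTCAE grading system, the information will be summarized using a shift table", both by visit and at the worst grade in the DBTP. It adds: "Numbers and cumulative numbers over decreasing toxicities grading of participants with treatment-emergent toxicities will also be shown".

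**Which outputs.** Table 24 lists two shift tables each for chemistry (14.3.4.1.2 by reference range, 14.3.4.1.3 by grade) and hematology (14.3.4.1.5 and 14.3.4.1.6). Coagulation has a descriptive summary, 14.3.4.1.7, and one shift table, 14.3.4.1.8: "Coagulation - Shift table of References Ranges versus Baseline on Clinical Findings during DBTP and Safety Follow-up period".

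**The concern.** Under 6.4.2, INR belongs to the graded group and is outside the reference-range group. Table 24 puts it in the reference-range group only. Table 14.3.4.1.8 therefore has no parameter that qualifies for it, and the table that 6.4.2 requires for INR has no number. A programmer working from the output list would leave out a promised analysis. One working from 6.4.2 would have nothing to put in 14.3.4.1.8.

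The choice changes the safety result as well as the layout. Clinical laboratory variables are among the primary endpoints (section 3.1), and the two rules can give opposite answers on whether the same INR change is treatment-emergent.

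**Working it through.** The plan states no figure to reproduce. The check sets the two rules side by side for the same INR values.

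**Inputs**

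- Reference-range rule (6.4.2): High if above 1.0 x ULN. A value is treatment-emergent if it goes from normal to low or high, from low to high, or from high to low. High to High does not count.
- Grade rule (6.4.2): "Treatment-emergent toxicity grade values are defined as laboratory values with higher grade post-baseline compared to the grade at baseline".
- Grade cut points for INR (Table 12): grade 0 up to 1.2, grade 1 above 1.2 to 1.5, grade 2 above 1.5 to 2.5, grade 3 above 2.5, all in multiples of ULN. I take the multiplier to apply to both ends of each interval, as it must in the ALT row (>1-3 x ULN).
- The SAP gives no INR reference range, so values are expressed in multiples of ULN. A value of 0.9 x ULN is assumed to lie within the normal range.

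**Classification of illustrative changes, baseline to post-baseline**

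| INR (x ULN) | Range shift | Treatment-emergent by range | Grade shift | Treatment-emergent by grade |
|---|---|---|---|---|
| 0.9 to 1.1 | Normal to High | yes | 0 to 0 | no |
| 0.9 to 1.3 | Normal to High | yes | 0 to 1 | yes |
| 1.1 to 1.3 | High to High | no | 0 to 1 | yes |
| 1.1 to 1.6 | High to High | no | 0 to 2 | yes |
| 1.1 to 2.6 | High to High | no | 0 to 3 | yes |
| 1.3 to 2.6 | High to High | no | 1 to 3 | yes |

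**Reading the table**

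1. A participant with normal baseline whose INR rises to more than 1.0 and at most 1.2 x ULN is treatment-emergent by range only.
2. A participant already above ULN at baseline cannot become treatment-emergent by range through any further rise, whatever the grade reached.
3. From a normal baseline, grades 1, 2 and 3 all fall in the same cell, Normal to High.

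The first effect does not arise for the other Table 12 tests graded upward in multiples of ULN (ALT, ALP, AST, total bilirubin, creatine kinase, creatinine). Their grade 1 starts just above 1.0 x ULN, so High and grade 1 or more coincide. INR is the exception because its grade 1 starts above 1.2.

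**Is it an extraction or redaction gap?** It does not look like one. The laboratory tables in Table 24 run from 14.3.4.1.1 to 14.3.4.1.12 without a break. Listing 16.2.8.1.3 selects coagulation participants by abnormality or toxicity grade of at least 1, whereas the urinalysis listing 16.2.8.1.4 uses abnormality alone. The plan elsewhere does treat INR as graded.

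**The case against.** The strongest reply is that the analysis is already planned. Section 6.4.2 requires grade shifts and treatment-emergent counts for every gradable test and does not exempt INR, so only an appendix entry is wrong. That stands. A reader might infer that INR toxicity will never be tabulated, but the document supports this only of the output list.

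A reader might also infer a second defect, that the plan defines abnormal in two ways. It does not. Each rule in 6.4.2 has its own set of tests and INR falls under one of them. The gap between 1.0 and 1.2 x ULN matters only if 14.3.4.1.8 is applied to INR, so it is a consequence of the one listing error.

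Nor would a marked rise necessarily be hidden. Table 14.3.4.1.7 gives INR by visit, including the maximum (section 6.2.1), and Listing 16.2.8.1.3 shows individual results. This stands in part. A by-visit maximum does not show the same participant's baseline or grade, and visits with fewer than 15 participants overall are not displayed. The listing is not a count by arm, and Table 25 marks it for interim analysis 1 and the final analysis but not for interim analysis 2. No output listed for interim analysis 2 therefore shows INR grades.

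Finally, this is one parameter in an exploratory trial of 48 participants without formal testing, and nothing in the SAP indicates how many would be affected. That limits the weight of the point but does not remove the contradiction.

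**Conclusion.** The point holds as an internal contradiction: section 6.4.2 with Table 12 requires a grade shift table for INR, and Table 24 lists a reference-range shift table instead. It concerns the only coagulation test. If Table 24 is followed, the by-arm shift output can miss worsening up to grade 3 in a participant above ULN at baseline, and can count a rise that stays at grade 0.

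The conclusion rests on reading the Table 12 cut points as multiples of ULN. It does not depend on any particular ULN. How often it would matter cannot be estimated from the document. It is worth correcting because laboratory variables are primary safety endpoints and the cost is small. No efficacy analysis is affected.

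**What to change.** In Table 24, replace 14.3.4.1.8 with a coagulation shift table of toxicity grades against baseline for the DBTP, covering INR, with worst-grade and treatment-emergent rows as in 14.3.4.1.3 and 14.3.4.1.6. If a reference-range view of INR is also wanted, keep 14.3.4.1.8 in addition and state the exception in 6.4.2.

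Settle the period in the coagulation titles at the same time. Tables 14.3.4.1.7 and 14.3.4.1.8 include the safety follow-up, unlike the chemistry, hematology and urinalysis tables, while section 6.2.1 says follow-up data are only listed. The sentence after Table 11 that has laboratory parameters summarized in both periods should be brought into line with this.

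The cost is one table shell with existing code and a few words of text. No new data are needed.

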**Table 14 Low, Normal and High Ranges for ECG parameters (Heart rate, PR and QRS)**

Parameters	Range		
	Low	Normal	High
Heart rate (beats/min)	< 40	40 -100	> 100
PR (ms)	< 120	120 – 220	> 220
QRS (ms)	< NA	0-120	> 120

NA: Not Applicable

Treatment-emergent out-of-range values are defined as follows :

- with normal values at baseline and low or high value at any post baseline visit, or
- with low values at baseline and high at any post baseline visit, or
- with high values at baseline and low at any post baseline visit.

If baseline is missing any postbaseline abnormality will be considered treatment-emergent.

For QTcB and QTcF (ms), the following categories will be derived:

- For the actual values: ≤ 450 (normal), ]450 ;480], ]480 ; 500], and > 500
- For the change from baseline: ≤ 30 (normal), ]30;60] and > 60.

For QTcB and QTcF, a treatment-emergent abnormality is defined as any postbaseline abnormality which was not present at baseline or which worsened following baseline (eg, QTcF ]450; 480] ms at baseline and >500 ms postbaseline). If baseline is missing any postbaseline abnormality will be considered treatment-emergent.

ECG parameters (heart rate, PR, QRS, QT, QTcB and QTcF intervals) will be summarized using actual value and change from baseline at each visit/time point by treatment group and overall in the SAF set on the DBTP.

For heart rate, PR and QRS, shift tables will also be created to summarize the number and proportion of participants with shifts from baseline category to “Low”, “Normal”, “High”, treatment-emergent by treatment group and visit . Shift tables from baseline to worst post DBTP baseline category will also be presented. In case of low and high post- baseline values, a category ‘low + high’ will be defined.

All ECG data for participants with post baseline abnormalities will be listed.

For QTc, shift tables will be created to summarize the number and proportion of participants with shifts from baseline to all visits according to the abnormality by treatment group and visit. Shift tables from baseline to worst post DBTP baseline abnormality will also be presented. Numbers and cumulative numbers of participants with treatment-emergent abnormalities will also be shown.

Abnormalities of QTc changes will be summarized at each post-baseline analysis visit and at the worst-post-Baseline analysis visit. Number and Cumulative numbers of participants with change abnormalities will also be shown.

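### Hemoglobin has no row in the toxicity-grading table, so a further fall in a participant already low at baseline is neither graded nor flagged as treatment-emergent

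*SAP*

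**What the plan says.** Section 3.1 of the SAP counts clinical laboratory variables among the primary safety endpoints. Section 6.4.2 sets out how they are analysed:

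- **Collection.** The hematology block of Table 11 lists hemoglobin, in g/L.
- **Grading.** CTCAE version 5.0 is the basis, and "CTCAE grades will be programmatically derived as described in the Table 12 when applicable". Table 12 is headed "Toxicity Grading for Selected Laboratory Tests". Its hematology rows are white cells ("White blood cells giga/L <LLN-3 <3-2 <2-1 <1"), platelets ("Platelets giga/L <LLN-75 <75-50 <50-25 <25"), neutrophils (low) and lymphocytes (low and high). Hemoglobin has no row in either direction.
- **Tests without grades.** Results are classed Low, Normal or High against the central laboratory's range. "Treatment-emergent out-of-range values are defined as laboratory values" that move from normal to low or high, from low to high, or from high to low. With a missing baseline, any post-baseline abnormality counts.
- **Tests with grades.** Treatment-emergent means "laboratory values with higher grade post-baseline compared to the grade at baseline", so a rise in grade from an already abnormal baseline counts.

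Section 6.4.4 treats QTc in a similar way to the graded tests, counting "any postbaseline abnormality which was not present at baseline or which worsened following baseline".

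**The concern.** Platelets and hemoglobin are reported in the same hematology panel but judged by different logic. A participant who starts with low platelets and falls into a worse grade is flagged. A participant who starts with low hemoglobin and falls further cannot be flagged, because Low is the only category available on that side. The group for whom the rule is blind is the group that starts below range, where an on-treatment decline would most need to be seen by severity.

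The modification history for SAP 3.0 shows that worsening from an abnormal baseline was thought worth counting. It records that the graded rule no longer requires grade 0 at baseline, and that a definition including worsening was added for QTc. I cite this for intent only. Hemoglobin misses the change because it has no row in Table 12.

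There is also a routing ambiguity. The definitions in section 6.4.2 divide tests by whether they have grades in Table 12. The paragraphs on shift tables, after Table 12, divide them by whether they can be graded under NCI CTCAE. For a test absent from Table 12 the two criteria could point different ways, and a programmer would have to choose.

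**Working it through.** The plan states no figure on this point, so there is none to reproduce. The check is a comparison of two tables and an enumeration of the rule.

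**Step 1. Table 11 against Table 12, hematology.**

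- Graded: white blood cells, neutrophils, lymphocytes, platelets.
- Not graded: hemoglobin, red blood cells, hematocrit, MCV, MCH, reticulocytes, eosinophils, basophils, monocytes.

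**Step 2. The reference-range rule over all nine pairs (baseline present).**

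| Baseline | Post: Low | Post: Normal | Post: High |
|---|---|---|---|
| Low | not flagged | not flagged | flagged |
| Normal | flagged | not flagged | flagged |
| High | flagged | not flagged | not flagged |

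Four of nine pairs are treatment-emergent. Low to low is not one of them, and the size of the fall does not enter the rule.

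**Step 3. Hemoglobin values.** The SAP gives no reference limit, so the limits and values here are assumptions.

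- Lower limit 120 g/L, baseline 118, worst 75: a fall of 118 − 75 = 43 g/L, Low to Low, not flagged.
- Lower limits of 115, 120, 130 and 135 g/L, baseline 1 or 10 g/L below the limit, post-baseline 100, 80, 60 or 40 g/L: 4 × 2 × 4 = 32 cases, none flagged.

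**Step 4. The same pattern in a graded test.** Assume a platelet lower limit of 150 giga/L and use the Table 12 bands. A fall from 140 to 20 goes from grade 1 to grade 4 and is flagged. A fall from 140 to 76 stays within grade 1 and is not. Grading therefore catches worsening that crosses a grade boundary, not every worsening.

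**Step 5. Where the hemoglobin fall can still be seen.**

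- Value and change from baseline by visit (section 6.4.2, Table 14.3.4.1.4). Section 6.2.1 includes the minimum among the statistics.
- Hematology Listing 16.2.8.1.2, which covers participants with a post-baseline abnormality and is marked for interim analysis 1 and the final analysis.
- The adverse event tables, if the investigator reports the event.

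These displays have limits. Section 5.5 takes the value closest to the target day in each window, so an off-schedule low point may not reach the by-visit summary. Section 6.2.1.3 brings unscheduled values into the worst-case visit, but the worst-case display that section 6.4.2 specifies for an ungraded test is the category shift, which shows only Low.

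**The case against.** The best case for the plan is that this is a choice and not a mistake. Table 12 is expressly a selection. The same three-condition rule governs vital signs in section 6.4.3 and heart rate, PR and QRS in section 6.4.4, so range-only parameters are treated alike. QTc and the graded tests have ordered severity bands in which worsening can be defined; a three-level scale has none. Hemoglobin is also not alone, since red cell count, hematocrit and several other tests are ungraded. Much of this stands: the SAP does not contradict itself in the rule, and the limit is general. What remains is that no reason is given for leaving hemoglobin out while the other main blood counts were selected.

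Stronger readings are tempting, but the documents do not support them:

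- *The fall is missed altogether.* It is not. It is unflagged and ungraded, but the change summaries, the listing and adverse event reporting remain.
- *The range rule is peculiar in counting a trivial crossing of the lower limit.* It is not. The low-direction hematology rows of Table 12 start at the lower limit of normal, in grade 1, so grading in the same way would count such a crossing too.
- *Reported abnormality rates will be wrong by a calculable amount.* The SAP says nothing about how many participants start low, and the values in the example are assumed.
- *Graded tests count all worsening.* They count only a rise in grade.

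**Conclusion.** The point holds as a limited one. Read literally, section 6.4.2 produces treatment-emergent counts and worst-case shifts for hemoglobin that cannot show a marked further fall in a participant already below range at baseline. This follows from the rule itself and does not depend on the assumed reference limit. Red cell count and hematocrit share the limit.

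The practical size is unknown. It depends on how many participants enter low and then decline, and the SAP gives no basis for estimating either. Because other displays would still carry the fall, the consequence is a weaker safety table within a primary endpoint, not a hidden signal. I rate it as a worthwhile, low-priority improvement.

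**What to change.** 1. Add a low-hemoglobin row to Table 12, using the hemoglobin criteria of CTCAE version 5.0, the version section 6.4.2 already adopts. The SAP does not state these cut-offs, so the sponsor should confirm them from the source. If not every grade can be derived from values, a partial row is consistent with the table: INR and high lymphocytes already have no grade 4.
2. Let hemoglobin enter the hematology grade shift, Table 14.3.4.1.6, by visit and for worst post-baseline grade, together with the existing treatment-emergent rule for graded tests.
3. State that the reference-range shift, Table 14.3.4.1.5, is kept for high hemoglobin, since the new row would cover the low direction only.
4. Use one criterion throughout section 6.4.2 for which tests are graded, preferably presence in Table 12, in both the definitions and the shift-table paragraphs.

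The cost is one table row, one parameter in a planned output and a wording change. No new data or new table is needed. Because the cohorts are unblinded at the interim locks, the modification history should record the date of the change and the reason for it.
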